**Description of Study Intervention/Experimental Manipulation:**

*12 week virtual workshop (offered via zoom) that covers behavioral skills including goal setting, self-monitoring, problem solving, contingency management, coping skills, and social support. Workshop topics included explanation of pre-diabetes/diabetes, label reading, healthy plate planning, portion control, finding affordable healthy foods, strategies to increase physical activity, and coping with eating triggers and social pressures. Participants create and report on action plans with weekly goals, brainstorm to solve problems, and communicate between sessions.*

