## 4 STUDY DESIGN

### 4.1 OVERALL DESIGN

We are now testing and evaluating outcomes of our refined intervention to reduce diabetes risk among ethnic minority pre-diabetic adolescents. We will further adapt the program for virtual delivery via a video conferencing platform to enhance access and attendance, and refine the text messaging platform to better support and engage teens.

We will identify at risk for diabetes adolescents and recruit adolescents (BMI in the overweight/obese range and HbA1c 5.7-6.4%) through electronic medical record data queries and referrals from clinical and community sites. Participation will be contingent on adolescent assent/parental consent (ages 13-17) or participant consent (ages 18 years or older). We will randomize pre-diabetic adolescents into intervention and wait list control (delayed intervention) groups to test intervention effectiveness. We will also evaluate the virtual and mHealth components of the intervention through usability testing and data analytics.

The intervention is 12 weekly 90-minute workshops based on feedback from our community advisory board and experts in peer led health education programs. The intervention will be offered via an online platform, Zoom, which is HIPAA compliant. We are testing the effectiveness of a virtual component versus our previous in-person workshop.

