We will obtain only the minimum amount of PHI necessary to contact potentially eligible teenagers. We will meet with providers and ask them to consent to contacting their patients who they think may be eligible. Contact information will be immediately deleted from the server for those who are not interested in participating or who are not eligible for the study. Participants will be given the opportunity to decline being re-contacted should they not be interested in participating.

For Collaborating Community sites – As described above, site leaders will verbally inform potential subjects about TEEN HEED and provide interested children with a letter for parents. For adolescents ages 18 or 19 years who meet eligibility requirements and are interested in the study, we will obtain informed consent prior to participation in the study. For adolescents ages 13-17 years, who meet eligibility requirements and are interested in the study, we will obtain assent of the adolescent and obtain consent from his/her parent or guardian. The combined Parental Consent and HIPAA Authorization Form will be obtained in person or over the phone by a member of the study staff. After consent is obtained, we will invite adolescents for their official baseline visit. Eligible adolescents will be randomized into intervention and wait list control groups. Intervention participants will attend a 12-week peer led workshop and follow up assessments.

We will recruit potential peer leaders through our contacts at community youth organizations in East and Central Harlem and local schools. Peer leaders will attend training sessions, workshop

sessions and debriefing sessions. All classes will be led by trained adolescent peer leaders. Qualifications to be a peer leader are: 1) older than 18 years of age 2) fluency in English and 3) ability to communicate well in a group setting. Peer leader training will include information about not divulging information (e.g., conditions, treatments, personal background or any other confidential or non-public information) concerning participants attending the classes. We will also have the leaders sign a Statement of Confidentiality. Peer leaders will be paid \$100 to attend the training session and \$300 for leading each 12 week workshop

Participants will be given a \$40 gift card at each study visit as compensation for their time.

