## 6 STUDY INTERVENTION(S) OR EXPERIMENTAL MANIPULATION(S)

### 6.1 STUDY INTERVENTION(S) OR EXPERIMENTAL MANIPULATION(S) ADMINISTRATION

#### 6.1.1 STUDY INTERVENTION OR EXPERIMENTAL MANIPULATION DESCRIPTION

Teen-led workshops cover behavioral skills including goal setting, self-monitoring, problem solving, contingency management, coping skills, and social support. Workshop topics include explanation of pre-diabetes/diabetes, label reading, healthy plate planning, portion control, finding affordable healthy foods, strategies to increase physical activity, and coping with eating triggers and social pressures. Participants create and report on action plans with weekly goals, brainstorm to solve problems, and communicate between sessions. The intervention is 12 weekly 90-minute workshops based on feedback from our community advisory board and experts in peer led health education programs. The intervention will be offered via an online platform, Zoom, which is HIPAA compliant. We are testing the effectiveness of the virtual program.

For participants in the text message pilot program we will obtain parental permission to allow mPulse Mobile to receive their cell phone numbers and send SMS text messages to participants. This information will be included in the study consent form with a separate place within the consent form for parents to initial to give this permission. Participants aged 18-19 will be asked to sign their own permission to receive SMS text messages from mPulse Mobile. We will make it very clear to participants that what is shared through the mobile dialogue is private, secure, and not shared with anyone beyond the program. We will also express that standard data and messaging rates from participant's provider may apply and that they can request that messages stop being sent at any time. Participants in the waitlist control will also be asked to consent to giving their phone numbers to mPulse

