#### 6.1.2 ADMINISTRATION AND/OR DOSING

Full-Dose: Attendance to all 12 workshops

Half-dose: Attendance to 6-11 workshops

Participants attending less than 4 workshops will be considered as "not adhering to the project"; however, they will not be removed from the study.

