## 9.2 SAMPLE SIZE DETERMINATION

## 9.3 POPULATIONS FOR ANALYSES

## 9.4 STATISTICAL ANALYSES

### 9.4.1 GENERAL APPROACH

We will use descriptive statistics to summarize the variables. Analyses will primarily test the hypothesis that intervention participants will have maintenance/reduction of BMI. Secondary analyses will assess whether the intervention leads to improvements in diet and physical activity behaviors and related mediators such as knowledge, attitudes, beliefs, self-efficacy, and social influences. Hypotheses will be tested by comparing changes in outcomes between baseline and follow up. Initial bivariate comparisons will use t tests to compare continuous endpoints and the Wilcoxon matched pairs signed-rank test to compare ordinal endpoints. We will then conduct multivariable analyses (using logistic regression, general linear models, and mixed models) to adjust for potential confounders (such as age, race/ethnicity, gender, SES, and baseline BMI) and to account for the repeated observations per participant. Analyses will include the baseline level of each endpoint as a covariate and a continuous variable for time. Confidence intervals will be constructed around each parameter estimate of the intervention. We will estimate effect sizes for each measure using correction for small sample bias.

To monitor the community-academic partnership, we will track activities such as the communication between community-academic partners, number of participants at CAB meetings, number of manuscripts and presentations by academic-community partners, and policy-related outcomes. We will also ask CAB members to complete annual surveys to gauge how closely the research project aligns with principles of CBPR, including factors they may feel less comfortable discussing in a group, such as level of inclusion and trust.

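### Section 9.4.1 allows for repeated measures on a participant but not for workshop group, so intervals are too narrow and p-values too small if the workshop ICC of the change is above zero

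*Combined protocol and SAP*

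**What the plan says.** Section 9.4.1 holds all the analysis detail on this point; Sections 9.2, 9.3, 9.4.2 and 9.4.3 have headings but no text. The first-line tests are these: "Initial bivariate comparisons will use t tests to compare continuous endpoints and the Wilcoxon matched pairs signed-rank test to compare ordinal endpoints". Logistic, general linear and mixed models follow, with two stated purposes: adjustment for confounders (age, race/ethnicity, gender, SES and baseline BMI are the examples) "and to account for the repeated observations per participant". The output is inferential: "Confidence intervals will be constructed around each parameter estimate of the intervention".

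Delivery is in groups. Section 4.1 states: "The intervention is 12 weekly 90-minute workshops". Section 5.1 requires that a teen can take part in a group class. Section 5.5 adds: "All classes will be led by trained adolescent peer leaders". Section 6.1.1 says that participants "brainstorm to solve problems, and communicate between sessions".

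No section mentions a workshop, cohort or leader effect, an ICC, a design effect or a cluster-robust standard error.

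**The concern.** Teens in one workshop have the same leaders, hear the same sessions and influence one another. Section 4.2 presents peer influence as the reason for the design. Their changes in BMI and behaviour may therefore be more alike than those of teens in different workshops. If so, a workshop of m teens carries less information than m independent teens, and a standard error computed from individual teens is too small.

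A participant-level term does not deal with this. It handles several visits by one teen, not several teens in one workshop. The t tests and signed-rank tests have no place for a workshop term at all. At stake is the precision claimed for this study's BMI and behaviour results.

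**Working it through.** The plan states no sample size, power, alpha or ICC, so it has no figure of its own to reproduce.

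**Inputs**
- Enrolled per workshop: 10 to 15 (Section 2.2, earlier in-person cohort; assumed to carry over to the virtual groups).
- Retention: 73% (Section 2.2, same cohort). Analysed per workshop: 0.73 × 10 = 7.3 and 0.73 × 15 = 10.95, so m is about 7 to 11.
- ICC of the change: not in the documents; 0.01, 0.05 and 0.10 assumed.
- Error level: not in the documents; two-sided 5% assumed.

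**Single arm, everyone in a workshop.** Design effect D = 1 + (m − 1) × ICC. The standard error is understated by √D, and the true error of the nominal 5% test is 2 × [1 − Φ(1.96/√D)].

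**Two equal arms, only the intervention arm grouped.** The variance ratio is (D + 1)/2, which replaces D in the same formula.

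| m | ICC | D | √D | Error, single arm | (D + 1)/2 | Error, two arms |
|---|---|---|---|---|---|---|
| 7 | 0.01 | 1.06 | 1.03 | 5.7% | 1.03 | 5.4% |
| 7 | 0.05 | 1.30 | 1.14 | 8.6% | 1.15 | 6.8% |
| 7 | 0.10 | 1.60 | 1.26 | 12.1% | 1.30 | 8.6% |
| 11 | 0.01 | 1.10 | 1.05 | 6.2% | 1.05 | 5.6% |
| 11 | 0.05 | 1.50 | 1.22 | 11.0% | 1.25 | 8.0% |
| 11 | 0.10 | 2.00 | 1.41 | 16.6% | 1.50 | 11.0% |

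At ICC 0, D = 1 and the error is 5% in every row.

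**Check by simulation.** With 4 workshops of 10, ICC 0.05 and workshop ignored, the simulated single-arm t test rejects in 10.1% of 40,000 runs. The formula at m = 10 gives D = 1.45 and 10.4%. The signed-rank test rejects in 9.9%. A two-arm logistic comparison against 49 ungrouped controls rejects in 7.3%. The direction is therefore not peculiar to the t test.

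**Unequal workshops.** The mean size understates D when sizes differ. Take sizes 4, 7, 13 and 16: the mean is 10, giving D = 1.45 at ICC 0.05. The size-weighted value is m* = Σm²/Σm = 490/40 = 12.25, giving D = 1 + 11.25 × 0.05 = 1.56.

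**Can a random effect cope with few workshops?** The earlier intervention arm of 41 teens at 10 to 15 per group makes about 3 or 4 workshops. With k workshops of m teens, the ANOVA workshop variance is zero or negative with probability P[F(k − 1, k(m − 1)) < (1 − ICC)/(1 − ICC + m × ICC)]. At ICC 0.05 and m of 7 to 11 this is 40% to 46% with 4 workshops, 23% to 32% with 10 and 12% to 22% with 20. A zero estimate returns the unadjusted analysis. An analysis of workshop means with 3 or 4 workshops has only 2 or 3 degrees of freedom, and its interval is about 1.6 to 2.1 times as wide even at ICC 0.

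**The case against.** - **Mixed models are already named and could carry a workshop term.** They could, but the text gives them two purposes and workshop is neither. The t tests and signed-rank tests could not carry one.
- **Every size above is hypothetical.** This stands. The ICC may be zero, and at ICC 0.01 the error is close to nominal. Only the conditional direction follows from the documents.
- **A reader might use the enrolled 10 to 15 per group and infer an error of up to 20.6%.** Section 2.2 does not support that for an analysis of follow-up data, because the cohort that gives the group size also gives 73% retention. On the analysed sizes the single-arm maximum is 16.6%.
- **A reader might infer that overstated precision would pass into the larger RCT.** The Synopsis (Study Description, third aim) bases refinement for that trial on feasibility, acceptability and sustainability. No section uses these intervals to size it or to decide whether it goes ahead.
- **It is a pilot, with perhaps too few workshops for a random effect.** The second half stands and shapes the fix. The first half does not remove the point, because Section 9.4.1 still tests hypotheses and plans intervals for the intervention estimates.

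**Conclusion.** The omission is clear from the text, and its consequence is conditional: with a workshop ICC above zero, intervals are too narrow and p-values too small. This holds in either design the protocol describes. Sections 4.1 and 5.5 describe randomised wait-list arms and Section 6.3 says there is no randomisation. These must be reconciled to know whether all participants or only the intervention arm are grouped, but the direction is the same.

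The size is illustrative. For 7 to 11 analysed per workshop, the single-arm error is 5.7%–6.2%, 8.6%–11.0% and 12.1%–16.6% at ICC 0.01, 0.05 and 0.10, with the standard error understated 1.03 to 1.41 times. With two equal arms it is 6.8%–8.0% at ICC 0.05 and at most 11.0% at ICC 0.10. These figures rest on the earlier cohort's group size and retention, an assumed ICC and an assumed two-sided 5% level. The consequence is limited to possibly overstated precision in this study's own BMI and behaviour results.

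**What to change.** 1. Record each participant's assigned workshop. Include low attenders, of whom Section 6.1.2 says "they will not be removed from the study".
2. Add to Section 9.4.1: *Analyses of workshop participants will account for workshop group (intervention arm only if controls are ungrouped).*
3. Fix in advance the number of workshops at which a random effect is used; about 10 is a reasonable threshold. At or above it, use a workshop random effect with small-sample degrees of freedom for continuous endpoints and a cluster-aware equivalent for binary and ordinal ones.
4. Below it, keep the planned analysis and label its intervals and p-values exploratory. Beside each primary interval, report a sensitivity range with the standard error multiplied by √[1 + (m* − 1) × ICC] at ICC 0.01, 0.05 and 0.10, where m* is the sum of squared analysed workshop sizes divided by their sum. With two arms, inflate only the intervention-arm variance.
5. Report the estimated ICC with its interval when there is more than one workshop.

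The cost is analysis wording and one dataset variable. Under the sensitivity range a single-arm interval widens about 1.03 to 1.41 times. The inflation is right only if the stated ICC is near the true one. With a true ICC of 0.05, the error is 2 × [1 − Φ(1.96 × √(D stated/D true))]. For m of 7 and 11, stating 0.01 leaves 7.7% and 9.3%, and stating 0.10 gives 3.0% and 2.4%. That is why a range is reported and not one value. The threshold of 10 is a judgement, since the workshop variance can still be estimated as zero at that number.

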### 9.4.2 ANALYSIS OF THE PRIMARY ENDPOINT(S)

### 9.4.3 ANALYSIS OF THE SECONDARY ENDPOINT(S)

### 9.4.4 SAFETY ANALYSES

### 9.4.5 BASELINE DESCRIPTIVE STATISTICS

Demographics: Age, Sex, BMI, Height, Weight, Waist Circumference, etc.

### 9.4.6 PLANNED INTERIM ANALYSES

N/A

### 9.4.7 SUB-GROUP ANALYSES

**Evaluation of the intervention's impact on the primary study outcome, participants' weights:** We hypothesize that the TEEN HEED intervention will result in maintenance or decrease in BMI percentile. We chose this outcome because weight loss is consistently shown as the most powerful and effective diabetes prevention strategy.

Evaluation of the effectiveness of the TEEN HEED intervention on behaviors and mediators related to weight loss and diabetes prevention: We hypothesize that the intervention will lead to observable changes to diet, physical activity and weight control behaviors and that these and other mediators explain weight loss. We will assess whether the intervention leads to improvements in diet and physical activity behaviors and related mediators such as knowledge, attitudes, beliefs, self-efficacy, and social influences, and improvements in other measures of diabetes risk (such as HbA1c). Hypotheses will be tested by comparing changes in outcomes between baseline and post-intervention follow-up. We will also conduct exploratory analyses to begin to understand whether any of these factors appear closely linked to pre-diabetes diagnosis or weight loss.

#### 9.4.8 TABULATION OF INDIVIDUAL PARTICIPANT DATA

- We aim to Recruit and enroll adolescents from clinical and community sites starting in the Spring 2021. Provisions may be made depending on the novel coronavirus pandemic.

#### 9.4.9 EXPLORATORY ANALYSES

We hypothesize that the intervention will lead to observable changes to diet, physical activity, and weight control behaviors and that these, and other, mediators explain weight loss. We will also conduct exploratory analyses to begin to understand whether any of these factors appear closely linked to pre-diabetes

### 10 SUPPORTING DOCUMENTATION AND OPERATIONAL CONSIDERATIONS

#### 10.1 REGULATORY, ETHICAL, AND STUDY OVERSIGHT CONSIDERATIONS

##### 10.1.1 INFORMED CONSENT PROCESS

###### 10.1.1.1 CONSENT/ASSENT AND OTHER INFORMATIONAL DOCUMENTS PROVIDED TO PARTICIPANTS

The study team will follow "SOP HRP -090 Informed Consent". Consent forms describing in detail the study intervention, study procedures, and risks will be given to the participant and written documentation of informed consent will be completed prior to starting the study intervention. The following consent materials are submitted with this protocol adult consent and parental consent in both English and Spanish.

###### 10.1.1.2 CONSENT PROCEDURES AND DOCUMENTATION

After participants are determined to be eligible for our study we will obtain informed consent over the phone, through REDCap, or in person. Due to the nature of the ongoing pandemic and many individuals limiting their exposure, multiple methods of obtaining consent are necessary.

##### 10.1.2 STUDY DISCONTINUATION AND CLOSURE

This study may be temporarily suspended or prematurely terminated if there is sufficient reasonable cause. Written notification, documenting the reason for study suspension or termination, will be provided by the suspending or terminating party to <study participants, investigator, funding agency, and regulatory authorities>. If the study is prematurely terminated or suspended, the Principal Investigator (PI) will promptly inform study participants, the Institutional Review Board (IRB), and sponsor/funding agency and will provide the reason(s) for the termination or suspension. Study participants will be contacted, as applicable, and be informed of changes to study visit schedule.

Circumstances that may warrant termination or suspension include, but are not limited to:

- Determination of unexpected, significant, or unacceptable risk to participants
- Demonstration of efficacy that would warrant stopping
- Insufficient compliance of study staff to the protocol (ie, significant protocol violations)
- Data that are not sufficiently complete and/or evaluable
- Determination that the primary endpoint has been met
- Determination of futility

The study may resume once concerns about safety, protocol compliance, and data quality are addressed, and satisfy the funding agency, sponsor, IRB, Food and Drug Administration (FDA), or other relevant regulatory or oversight bodies (OHRP, DSMB).

---

#### 10.1.3 CONFIDENTIALITY AND PRIVACY

Participant confidentiality and privacy is strictly held in trust by the participating investigators, their staff, the safety and oversight monitor(s), and the sponsor(s) and funding agency. This confidentiality is extended to the data being collected as part of this study. Data that could be used to identify a specific study participant will be held in strict confidence within the research team. No personally-identifiable information from the study will be released to any unauthorized third party without prior written approval of the sponsor/funding agency.

All research activities will be conducted in as private a setting as possible.

The study monitor, other authorized representatives of the sponsor or funding agency, representatives of the Institutional Review Board (IRB), regulatory agencies or representatives from companies or organizations supplying the product, may inspect all documents and records required to be maintained by the investigator, including but not limited to, medical records (office, clinic, or hospital) and pharmacy records for the participants in this study. The clinical study site will permit access to such records.

The study participant's contact information will be securely stored at each clinical site for internal use during the study. At the end of the study, all records will continue to be kept in a secure location for as long a period as dictated by the reviewing IRB, Institutional policies, or sponsor/funding agency requirements.

#### Measures Taken to Ensure Confidentiality of Data Shared per the NIH Data Sharing Policies

It is NIH policy that the results and accomplishments of the activities that it funds should be made available to the public (see <https://grants.nih.gov/policy/sharing.htm>). The PI will ensure all mechanisms used to share data will include proper plans and safeguards for the protection of privacy, confidentiality, and security for data dissemination and reuse (e.g., all data will be thoroughly de-identified and will not be traceable to a specific study participant). Plans for archiving and long-term preservation of the data will be implemented, as appropriate.

#### Certificate of Confidentiality

To further protect the privacy of study participants, the Secretary, Health and Human Services (HHS), has issued a Certificate of Confidentiality (CoC) to all researchers engaged in biomedical, behavioral, clinical or other human subjects research funded wholly or in part by the federal government. Recipients of NIH funding for human subjects research are required to protect identifiable research information from forced disclosure per the terms of the NIH Policy (see <https://humansubjects.nih.gov/coc/index>). As set forth in 45 CFR Part 75.303(a) and NIHGPS Chapter 8.3, recipients conducting NIH-supported research covered by this Policy are required to establish and maintain effective internal controls (e.g., policies and procedures) that provide reasonable assurance that the award is managed in compliance with Federal statutes, regulations, and the terms and conditions of award. It is the NIH policy that investigators and others who have access to research records will not disclose identifying information except when the participant consents or in certain instances when federal, state, or local law or regulation requires disclosure. NIH expects investigators to inform research participants of the protections and the limits to protections provided by a Certificate issued by this Policy.

---

